Dose reductions of atezolizumab are not permitted. Guidelines for treatment interruption or discontinuation and the management of specific adverse events related to the combination of cobimetinib and atezolizumab are provided in Sections 5.1.3 (see Table 6). Guidelines for treatment interruption or discontinuation and the management of atezolizumab-specific adverse events are provided in Section 5.1.2 and Appendix 8, as well as the Atezolizumab Investigator's Brochure. For anaphylaxis precautions, see Appendix 7.

See the Pharmacy Manual for detailed instructions on drug preparation, storage, and administration.

Any overdose or incorrect administration of atezolizumab should be noted on the atezolizumab administration eCRF. Adverse events associated with an overdose or incorrect administration of atezolizumab should be recorded on the Adverse Event eCRF (see Section 5.3.5.12).

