5. ASSESSMENT OF SAFETY

5.1 SAFETY PLAN

The safety plan for patients in this study is based on clinical experience with cobimetinib and atezolizumab in completed and ongoing studies and on published data from similar molecules. The anticipated important safety risks for cobimetinib and atezolizumab are

outlined below. Refer to the Cobimetinib Investigator's Brochure and Atezolizumab Investigator's Brochure for a complete summary of safety information.

Measures will be taken to ensure the safety of patients participating in this study, including the use of stringent inclusion and exclusion criteria and close monitoring of patients during the study. Eligibility criteria have been designed to exclude patients at higher risk for toxicities. Administration of atezolizumab will be performed in a monitored setting in which there is immediate access to trained personnel and adequate equipment and medicine to manage potentially serious reactions.

Patients will undergo safety monitoring during the study, including assessment of the nature, frequency, and severity of adverse events. In addition, guidelines for managing adverse events, including criteria for dosage modification, and treatment interruption or discontinuation, are provided below. There are separate guidelines for the three different arms as the toxicities and management guidelines are distinct. Refer to the specific guidelines for each arm individually.

The risks associated with cobimetinib and atezolizumab are detailed in Section 5.1.1 and 5.1.2, respectively. Additional information on the risks of atezolizumab and management of atezolizumab-related adverse events are outlined in Appendix 8

Adverse events will be reported as described in Sections 5.2–5.4. Oversight will be provided by the Medical Monitor and drug safety personnel.

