5.1.2 Risks Associated with Atezolizumab

Atezolizumab has been associated with risks such as *the following*: IRRs and immune-related hepatitis, pneumonitis, colitis, pancreatitis, diabetes mellitus, hypothyroidism, hyperthyroidism, adrenal insufficiency, Guillain-Barré syndrome, myasthenic syndrome or myasthenia gravis, meningoencephalitis, myocarditis, hypophysitis, *and* nephritis. In addition, systemic immune activation is a potential risk associated *when atezolizumab is given in combination with other immunomodulating agents*. Refer to [Appendix 8](#) of the protocol and Section 6 of the Atezolizumab Investigator's Brochure for a detailed description of anticipated safety risks for atezolizumab.

Systemic immune activation is a rare condition characterized by an excessive immune response. Given the mechanism of action of atezolizumab, systemic immune activation is considered a potential risk when administered in combination with other immunomodulating agents. Systemic immune activation should be included in the differential diagnosis for patients who, in the absence of an alternative etiology, develop a sepsis-like syndrome after administration of atezolizumab, and the initial evaluation should include the following:

- CBC with peripheral smear
- PT, PTT, fibrinogen, and D-dimer
- Ferritin
- Triglycerides
- AST, ALT, and total bilirubin
- LDH
- Complete neurologic and abdominal examination (assess for hepatosplenomegaly)

If systemic immune activation is still suspected after the initial evaluation, contact the Medical Monitor for additional recommendations. See [Appendix 8](#) for additional information on the diagnosis and management of systemic immune activation.

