5.1.3 Management of Patients Who Experience Specific Adverse Events

5.1.3.1 Cobimetinib Dose Modifications

General dose modifications for cobimetinib are provided in [Table 5](#). Dose modifications for specific adverse events are provided in [Table 6](#).

Table 5 Recommended Cobimetinib Dose Modifications

Grade (NCI CTCAE)	Recommended Cobimetinib Dose
Grade 1 or Grade 2 (tolerable)	No dose reduction. Maintain cobimetinib at the same dose of 60 mg QD (3 tablets)
Grade 2 (intolerable) or Grade 3 or 4 (any)	
First appearance	Interrupt treatment until Grade \leq 1, restart treatment at 40 mg QD (2 tablets)
Second appearance	Interrupt treatment until Grade \leq 1, restart treatment at 20 mg QD (1 tablet)
Third appearance	Consider permanent discontinuation.

NCI CTCAE=National Cancer Institute Common Terminology Criteria for Adverse Events;
QD=once daily.

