For Grade 4 CPK elevations that are asymptomatic and deemed not clinically significant	
 • Interrupt cobimetinib and atezolizumab treatment. • If improved to Grade ≤ 3 within 4 weeks, restart cobimetinib at a dose reduced by 20 mg, if clinically indicated. • If CPK elevations do not improve to Grade ≤ 3 within 4 weeks following dose interruption, permanently discontinue cobimetinib treatment. • Resumption of atezolizumab may be considered in patients who are deriving benefit.
Rhabdomyolysis or symptomatic CPK elevations	
 • Interrupt cobimetinib and atezolizumab treatment. • If severity is improved by at least one grade and symptoms resolve within 4 weeks, restart cobimetinib at a dose reduced by 20 mg, if clinically indicated. • If rhabdomyolysis or symptomatic CPK elevations do not improve within 4 weeks, permanently discontinue cobimetinib treatment • Resumption of atezolizumab may be considered in patients who are deriving benefit after discussion with the Medical Monitor.

CPK = creatine phosphokinase.

Table 6 Guidelines for Management of Patients Who Experience Specific Adverse Events (Cobimetinib and Atezolizumab) (cont.)

Event	Action to Be Taken
Hemorrhage	
Grade 3 hemorrhage	
 Interrupt cobimetinib treatment. There are no data on the effectiveness of cobimetinib dose modification for hemorrhage events. Clinical judgment should be applied when considering restarting cobimetinib treatment. Continue atezolizumab treatment.
Grade 4 hemorrhage or any grade cerebral hemorrhage	
 Interrupt cobimetinib treatment. Permanently discontinue cobimetinib for hemorrhage events attributed to cobimetinib. Continue atezolizumab treatment.
Grade 3 or 4 or intolerable Grade 2 treatment-related toxicities not described above and in Table 5 (dose modifications for cobimetinib)	
 Withhold all study treatment. If event resolves to Grade 1 or better within 105 days, resume atezolizumab at fixed dose. If not, permanently discontinue atezolizumab.^{a, b, c} If event resolves to Grade 1 or better within 28 days, resume cobimetinib with dose reduced by one level. If not, permanently discontinue cobimetinib.

^a If corticosteroids have been initiated, they must be tapered over ≥ 1 month to ≤ 10 mg/day oral prednisone or equivalent before atezolizumab can be resumed.

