^b Atezolizumab may be withheld for a period of time beyond 105 days to allow for corticosteroids to be reduced to ≤ 10 mg/day oral prednisone or equivalent. The acceptable length of the extended period of time must be agreed upon by the investigator and the Medical Monitor.

^c Resumption of atezolizumab may be considered in patients who are deriving benefit and have fully recovered from the immune-related event. Patients can be rechallenged with atezolizumab only after approval has been documented by both the investigator (or an appropriate delegate) and the Medical Monitor.

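### For at least seven immune-related events found only in Appendix 8, the Table 6 catch-all read literally restarts atezolizumab after recovery where Appendix 8 stops it for good; Section 4.5.3 also cites the wrong appendix

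*Combined protocol and SAP*

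**What the plan says.** Unless marked otherwise, Table 6 means the one in Section 5.1.3.3 of the protocol body; Appendix 8 numbers its own tables.

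- **Catch-all, last row of Table 6.** It covers "Grade 3 or 4 or intolerable Grade 2 treatment-related toxicities not described above and in Table 5". The first instruction is "Withhold all study treatment". The next is "If event resolves to Grade 1 or better within 105 days, resume atezolizumab at fixed dose", with permanent discontinuation if that recovery is not reached. Footnotes a to c are attached to this bullet. Footnote c says "Patients can be rechallenged with atezolizumab only after approval has been documented by both the investigator" and the Medical Monitor.
- **Table 5.** Its title is "Recommended Cobimetinib Dose Modifications". It gives no instruction for atezolizumab.
- **Appendix 8.** It sets actions for atezolizumab by event and grade. Several rows call for permanent discontinuation. The introduction to the appendix allows resumption as an exception, for a patient who is benefiting and has fully recovered, with documented approval from both the investigator and the Medical Monitor.
- **Routing text.** Section 4.2.2.2 sends events related to the combination to Table 6. It then says that stopping guidance and "the management of atezolizumab-specific adverse events are provided in Section 5.1.2 and Appendix 8". Section 5.1 says that "management of atezolizumab-related adverse events are outlined in Appendix 8". Section 5.1.2 lists the drug's risks and refers to Appendix 8 "for a detailed description of anticipated safety risks for atezolizumab". Section 5.1.3.3 points to Appendix 8 for atezolizumab-related events, then sends toxicities specific to cobimetinib and atezolizumab to Table 6.
- **Section 4.5.3.** Its list of reasons for mandatory permanent discontinuation includes adverse events that require it under Appendix 7. Appendix 7 is the anaphylaxis precautions.

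**The concern.** A Cohort A or B site facing, say, Grade 3 myocarditis finds no myocarditis row in Table 6. The last row of that table then appears to apply: the event is Grade 3, treatment-related and not described above. Followed as written, it makes restarting the default once the event is down to Grade 1. Appendix 8 instead treats the drug as permanently discontinued and restarting as an exception.

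The events concerned include some of the most dangerous immune-related toxicities, and the catch-all is the less cautious of the two instructions. A site that turns to the mandatory-stop list in Section 4.5.3 is sent to an appendix with no stopping criteria by event and grade.

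**Working it through.** No figure in the plan is involved, so the check is a side-by-side reading.

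**Step 1: what the catch-all exempts.** It exempts events described higher in Table 6 and in Table 5. Table 5 covers any Grade 3 or 4 event and intolerable Grade 2, but only for cobimetinib dosing. If it exempted all those events, the catch-all would cover nothing. Appendix 8 is not among the exemptions.

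**Step 2: Appendix 8 rows that discontinue permanently.** Thirteen graded rows make permanent discontinuation the default. Six concern events that have their own Table 6 row or a pointer from Table 6 to Appendix 8: pulmonary Grade 3-4, hepatic Grade 3-4, diarrhea or colitis Grade 4, ocular Grade 3-4, infusion-related reaction Grade 3-4 and dermatologic Grade 4. That leaves 13 − 6 = 7.

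| Appendix 8 event (default: permanent discontinuation) | Appendix 8 table | Overlap with the catch-all |
|---|---|---|
| Hypophysitis, Grade 4 | 4 | Full |
| Myocarditis, Grade 3-4 | 6 | Full |
| Pancreatitis, Grade 4 | 8 | Full |
| Neuropathy, Grade 3-4 | 10 | Full |
| Myasthenia gravis or Guillain-Barré, any grade | 10 | Grade 3-4 or intolerable Grade 2 only |
| Meningoencephalitis, all grades | 11 | Grade 3-4 or intolerable Grade 2 only |
| Renal event, Grade 3-4 | 12 | Full |

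Seven is a floor. The systemic immune activation row in Appendix 8 Table 13 (four or more major criteria) also discontinues permanently and has no Table 6 row. It is triggered by a count of criteria, not by grade; adding it gives 7 + 1 = 8.

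**Step 3: where the instructions differ.**

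| | Catch-all | Appendix 8 |
|---|---|---|
| At onset | Withhold | Stop |
| Default after recovery | Resume if recovered within 105 days | Remain off the drug |
| Recovery needed to restart | Grade 1 or better | Full recovery, with benefit, as an exception |
| Dual approval to restart | Unclear: footnote markers follow the sentence on permanent discontinuation | Required |

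The first line agrees. The second and third differ. The fourth depends on whether footnote c governs the resume instruction as well.

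**Step 4: is precedence stated?** The routing text in Sections 4.2.2.2, 5.1.2 and 5.1.3.3 favors Appendix 8, but none of it says which source prevails. Two statements keep the literal reading open: Section 5.1 tells sites to use the guidelines specific to each arm, and Section 5.1.3.3 sends atezolizumab-specific toxicities to Table 6. Where Table 6 hands over to Appendix 8, it says so, in the rows for infusion-related reactions and immune-related ocular toxicity. The catch-all has no such wording.

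**Step 5: Section 4.5.3.** Appendix 7 lists equipment and steps for a suspected anaphylactic reaction. It has no discontinuation guideline by event and grade. Those guidelines are in Table 6 and Appendix 8.

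**The case against.** The strongest reply is that the division of labor is already clear. Section 4.2.2.2 pairs two sentences: combination events to Table 6, atezolizumab-specific events to Appendix 8. Section 5.1.2 names six of the seven events, or their plain equivalents, as atezolizumab risks; only neuropathy in general is missing. A residual row does not naturally displace a named, graded row for the same event. This stands: Appendix 8 is the natural reading. It does not remove the defect, because the literal reading is also open and is the less cautious one.

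Safeguards narrow the practical gap, and this also stands. Footnote c may require dual approval under the catch-all too. Section 5.2.3 makes the same six events reportable to the sponsor within 24 hours, well before the 105-day window closes. Section 4.5.3 lets the sponsor end treatment for any condition that may endanger the patient.

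A reader might also infer that Table 6 and Appendix 8 conflict generally, since they differ on Grade 3 rash, Grade 3 AST/ALT elevation and tolerable Grade 2 diarrhea. The documents do not support counting these here. Each has its own Table 6 row, and each overlaps with known cobimetinib toxicity, so a separate combination rule is understandable. They say nothing about events that Table 6 leaves out.

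Nor would a correct reference in Section 4.5.3 settle the conflict. Citing Table 6 and Appendix 8 together sets no order between them, so the two corrections are separate.

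**Conclusion.** The point holds as a minor defect in the safety guidance for Cohorts A and B (about 90 + 12 = 102 patients). Cohort C receives monotherapy and lies outside the combination table. At least seven graded Appendix 8 rows have a more cautious default after recovery than the catch-all, two of them only at Grade 3-4 or intolerable Grade 2. The systemic immune activation row raises the same issue. One cross-reference is wrong.

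The conclusion rests on reading the catch-all literally, with Table 5 exempting nothing for atezolizumab. A reader might infer that patients would be kept on the drug through these events, or restarted with no oversight. The documents do not support that: both sources stop treatment at onset, and dual approval may apply under both. The documents give no incidence for these events in Cohorts A and B, so no number of affected patients can be stated. No efficacy estimate, adverse-event summary or other statistical result changes.

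**What to change.** Extend the scope of the catch-all row in Table 6 with: *and not covered in Appendix 8; where Appendix 8 has a row for the event and Table 6 does not, Appendix 8 governs atezolizumab*. Cobimetinib stays under Table 5 and the Table 6 general guidance. This wording also covers the systemic immune activation row.

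Separately, change the reference in Section 4.5.3 from Appendix 7 to Table 6 and Appendix 8.

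The cost is one phrase and one cross-reference, with no operational burden and no change to design or analysis.

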5.2 SAFETY PARAMETERS AND DEFINITIONS

Safety assessments will consist of monitoring and recording adverse events, including serious adverse events and adverse events of special interest, performing protocol-specified safety laboratory assessments, measuring protocol-specified vital signs, and conducting other protocol-specified tests that are deemed critical to the safety evaluation of the study.

Certain types of events require immediate reporting to the Sponsor, as outlined in Section 5.4.

5.2.1 Adverse Events

According to the ICH guideline for Good Clinical Practice, an adverse event is any untoward medical occurrence in a clinical investigation subject administered a pharmaceutical product, regardless of causal attribution. An adverse event can therefore be any of the following:

- Any unfavorable and unintended sign (including an abnormal laboratory finding), symptom, or disease temporally associated with the use of a medicinal product, whether or not considered related to the medicinal product

- Any new disease or exacerbation of an existing disease (a worsening in the character, frequency, or severity of a known condition), except as described in Section [5.3.5.10](#)
- Recurrence of an intermittent medical condition (e.g., headache) not present at baseline
- Any deterioration in a laboratory value or other clinical test (e.g., ECG, X-ray) that is associated with symptoms or leads to a change in study treatment or concomitant treatment or discontinuation from study drug
- Adverse events that are related to a protocol-mandated intervention, including those that occur prior to assignment of study treatment (e.g., screening invasive procedures such as biopsies)

5.2.2 Serious Adverse Events (Immediately Reportable to the Sponsor)

A serious adverse event is any adverse event that meets any of the following criteria:

- Is fatal (i.e., the adverse event actually causes or leads to death)
- Is life threatening (i.e., the adverse event, in the view of the investigator, places the patient at immediate risk of death)
 - This does not include any adverse event that had it occurred in a more severe form or was allowed to continue might have caused death.
- Requires or prolongs inpatient hospitalization (see Section [5.3.5.11](#))
- Results in persistent or significant disability/incapacity (i.e., the adverse event results in substantial disruption of the patient's ability to conduct normal life functions)
- Is a congenital anomaly/birth defect in a neonate/infant born to a mother exposed to study drug
- Is a significant medical event in the investigator's judgment (e.g., may jeopardize the patient or may require medical/surgical intervention to prevent one of the outcomes listed above)

The terms "severe" and "serious" are not synonymous. Severity refers to the intensity of an adverse event (e.g., rated as mild, moderate, or severe, or according to NCI CTCAE v4.0; see Section [5.3.3](#)); the event itself may be of relatively minor medical significance (such as severe headache without any further findings).

Severity and seriousness need to be independently assessed for each adverse event recorded on the eCRF.

Serious adverse events are required to be reported by the investigator to the Sponsor immediately (i.e., no more than 24 hours after learning of the event; see Section [5.4.2](#) for reporting instructions).

5.2.3 Adverse Events of Special Interest (Immediately Reportable to the Sponsor)

Adverse events of special interest are required to be reported by the investigator to the Sponsor immediately (i.e., no more than 24 hours after learning of the event; see Section 5.4.2 for reporting instructions). Adverse events of special interest for this study include the following:

- Significant liver toxicity
- Cases of potential drug-induced liver injury that include an elevated ALT or AST in combination with either an elevated bilirubin or clinical jaundice, as defined by Hy's Law (see Section 5.3.5.7) and based on the following observations:
 - Treatment-emergent ALT or AST $> 3 \times$ baseline value in combination with total bilirubin $> 2 \times$ ULN (of which $\geq 35\%$ is direct bilirubin)
 - Treatment-emergent ALT or AST $> 3 \times$ baseline value in combination with clinical jaundice
 - Hepatitis, including AST or ALT $> 10 \times$ ULN
- Suspected transmission of an infectious agent by the study drug, as defined below
 - Any organism, virus, or infectious particle (e.g., prion protein–transmitting transmissible spongiform encephalopathy), pathogenic or non-pathogenic, is considered an infectious agent. A transmission of an infectious agent may be suspected from clinical symptoms or laboratory findings that indicate an infection in a patient exposed to a medicinal product. This term applies only when a contamination of the study drug is suspected.
- Pneumonitis
- Colitis
- Endocrinopathies: diabetes mellitus, pancreatitis, adrenal insufficiency, hyperthyroidism, and hypophysitis
- Systemic lupus erythematosus
- Neurologic disorders: Guillain-Barré syndrome, myasthenic syndrome or myasthenia gravis, and meningoencephalitis
- Nephritis
- Events suggestive of hypersensitivity, infusion-related reactions, cytokine-release syndrome, influenza-like illness, systemic inflammatory response system
- Ocular toxicities
 - Uveitis
 - RVO
 - Serous retinopathy
 - Myositis

- Cardiac disorders for the following events:
 - Grade ≥ 2 cardiac disorders, including atrial fibrillation, myocarditis, and pericarditis
 - Symptomatic heart failure or Grade ≥ 3 reduction in LVEF
- Vasculitis
- Myopathies, including rhabdomyolysis or Grade ≥ 3 CPK elevation
- Grade ≥ 3 hemorrhage or any-grade cerebral hemorrhage
- Grade ≥ 3 rash
- Grade ≥ 3 diarrhea

5.3 METHODS AND TIMING FOR CAPTURING AND ASSESSING SAFETY PARAMETERS

The investigator is responsible for ensuring that all adverse events (see Section 5.2.1 for definition) are recorded on the Adverse Event eCRF and reported to the Sponsor in accordance with instructions provided in this section and in Sections 5.4–5.6.

For each adverse event recorded on the Adverse Event eCRF, the investigator will make an assessment of seriousness (see Section 5.2.2 for seriousness criteria), severity (see Section 5.3.3), and causality (see Section 5.3.4).

5.3.1 Adverse Event Reporting Period

Investigators will seek information on adverse events at each patient contact. All adverse events, whether reported by the patient or noted by study personnel, will be recorded in the patient's medical record and on the Adverse Event eCRF.

After informed consent has been obtained **but prior to initiation of study drug**, only serious adverse events caused by a protocol-mandated intervention (e.g., invasive procedures such as biopsies, discontinuation of medications) should be reported (see Section 5.4.2 for instructions for reporting serious adverse events).

After initiation of study drug, all adverse events will be reported until 90 days after the last dose of study drug. After this period, the investigator should report any serious adverse events that are believed to be related to prior study drug treatment (see Section 5.6).

